## Study size

The study is descriptive in nature and will apply until a maximum of 10 years from market authorization or until 500 prospectively reported live births with known status of malformations are assessed, whichever occurs first.

A sample size of 500 live births achieves 89% power to detect a prevalence increase of 3% using a two-sided binomial test for one sample proportion (significance level  $\alpha = 0.05$ ) assuming a background prevalence for major malformation of 3% as reported in the US ([CDC 2018](#)).

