### **7.1.2 Adjudication process**

The individual case safety report (ICSR) of with reported potential congenital anomaly, i.e. each individual case of reported congenital abnormality or other outcome (spontaneous abortion, elective termination or stillbirth) for which there is evidence of a birth defect, will undergo adjudication. These cases will be identified from the Novartis global safety database as cases with an AE with seriousness classification “congenital anomaly” and with fetal outcome coded as “congenital anomaly major”, “congenital anomaly minor” and “congenital anomaly NOS (structural)”.

The adjudication panel will consist of three independent external experts in the field of teratology or reproductive toxicology. Two of the three experts will perform the initial independent adjudication of individual case. The third expert will be contacted in case of different opinions by the two initial adjudicators.

Adjudicators will evaluate the data to determine whether the malformation was major, minor and/or of chromosomal origin using European Surveillance of Congenital Anomalies (EUROCAT) and Metropolitan of Atlanta Congenital Defects Program (MACDP) classification criteria.

The outcome per EUROCAT classification will be considered as the main classification entered in the Novartis global safety database accordingly. The MACDP classification will be kept in the notes. Reports with insufficient information for adjudication will be classified as “congenital anomaly not otherwise specified (NOS)”.

The full adjudication process, role and responsibilities and data handling will be described in a separate adjudication charter.

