### 7.7.1 Analysis of primary and secondary endpoints

Analysis of the Kesimpta-PRIM data will include estimation of proportion (and 95% confidence interval) of malformations (major [primary endpoint], minor [secondary endpoint], and overall), and of specific pregnancy outcomes such as, spontaneous abortions, stillbirths and elective terminations. The proportion of congenital malformations will be calculated amongst: (1) live births; and (2) live births, stillbirths and TOPFA (termination of pregnancy for fetal anomaly). Proportion will be estimated overall and by pre-specified timing of drug exposure in pregnancy (as defined in [Section 7.3.1](#)).

In addition, major congenital malformations will also be summarized by SOC based on latest available MedDRA classification.

Minor congenital malformations will be listed by preferred term based on latest available MedDRA classification.

The proportion of **other adverse birth outcomes** associated with exposure to Kesimpta during pregnancy including preterm births, low birth weight and small for gestational age (SGA) will be estimated among live births.

The proportion of adverse effects with particular focus on serious infections in the infant during the first 12 months after birth will be provided.

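### The only breakdown the readable protocol fixes for major malformations is by MedDRA SOC, coarser than the preferred-term listing for minor ones and probably poorly suited to show a cluster of one defect

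*Protocol*

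**What the plan says.** Protocol section 7.7.1 plans "estimation of proportion (and 95% confidence interval) of malformations (major [primary endpoint], minor [secondary endpoint], and overall"), plus proportions for other pregnancy outcomes. Malformations are counted over two denominators: live births, and live births with stillbirths and TOPFA. The further split of the estimate is by exposure window: "Proportion will be estimated overall and by pre-specified timing of drug exposure in pregnancy".

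On type of defect, 7.7.1 makes two commitments. For the primary outcome, "major congenital malformations will also be summarized by SOC based on latest available MedDRA classification". For the secondary outcome, "Minor congenital malformations will be listed by preferred term based on latest available MedDRA classification". The objectives in section 6.2 repeat the preferred-term listing for minor malformations. The objective for major malformations in section 6.1 has no counterpart.

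Section 7.1.2 describes adjudication: "Adjudicators will evaluate the data to determine whether the malformation was major, minor and/or of chromosomal origin". It then says "The outcome per EUROCAT classification will be considered as the main classification entered in the Novartis global safety database accordingly". It names no organ-system or defect subgroup as an output and refers to an adjudication charter that is not shown.

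**The concern.** A teratogenic effect may be confined to one kind of defect. The overall proportion of major malformations dilutes such an effect, so a reader looks to the defect-type table for it. Here that table is fixed at SOC, the top level of MedDRA, for the outcome that matters most, while the less important outcome gets preferred terms. The difference in level is visible in 7.7.1 alone.

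How much it matters depends on what a SOC row contains, which the protocol does not say. The assumption made here is MedDRA's usual primary-SOC convention, under which congenital anomaly terms sit in one congenital SOC whatever the organ. A heart defect, a cleft and a urogenital defect would then share a row, and the table would add little to the overall count. If secondary SOC paths were used, organ systems would separate, but the protocol does not commit to that.

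Section 6 says the findings will be used to evaluate potential reproductive toxicity under the RMP, and section 4 plans annual interim reports. The wording of 7.7.1 sets the minimum that those reports are bound to show.

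**Working it through.** **Inputs from the protocol.** N = 500 live births (section 7.5); background 3% and exposed 6% (section 7.5, Table 7-8); two-sided exact one-sample binomial test at 0.05, taken as at most 0.025 in each tail.

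**Inputs assumed for illustration.** Background of a single organ group: 0.1%, 0.2%, 0.5% or 1%. Excess due to exposure: one percentage point, all in that group. Number of groups screened: 10.

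**Step 1: reproduce the plan's figure.** With X ~ Bin(500, 0.03), the smallest c with P(X ≥ c) ≤ 0.025 is c = 24 (tail 0.0179). The lower region is X ≤ 7. Power at 6% is P(X ≥ 24 | 0.06) = 0.8926, which matches Table 7-8. All nine rows of that table reproduce. The concern disputes no printed figure.

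**Step 2: expected number of cases.** 500 × 0.03 = 15 major malformations at background. A case-by-case listing is therefore short.

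**Step 3: the pooled test when the excess sits in one group.** The total moves from 3% to 4%, and P(X ≥ 24 | 0.04) = 0.208 (0.209 with the lower tail). An excess of 0.8 points (3% to 3.8%) gives 0.148.

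**Step 4: the same excess seen in its own group.** For background p0, take the smallest c with P(X ≥ c | 500, p0) ≤ 0.025, then compute P(X ≥ c | 500, p0 + 0.01). For Bonferroni over 10 groups, replace 0.025 by 0.025/10 = 0.0025.

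| Assumed background | Cases needed, unadjusted | Power | Cases needed, 10 groups | Power |
|---|---|---|---|---|
| 0.1% | 3 | 0.913 | 4 | 0.800 |
| 0.2% | 4 | 0.850 | 6 | 0.555 |
| 0.5% | 7 | 0.623 | 9 | 0.338 |
| 1% | 11 | 0.417 | 13 | 0.207 |

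The pooled figure for comparison is 0.208. A separate group is more informative when its background is low. At 1% background with 10 groups the advantage has gone.

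**Step 5: single rare defects.** Unadjusted, a defect with an assumed 0.1% background (500 × 0.001 = 0.5 expected) stands out at 3 or more cases. The chance of that is 0.46 for a 5-fold increase and 0.88 for a 10-fold one. At 0.05% the chances are 0.13 and 0.46. At 0.2% (4 or more cases) they are 0.74 and 0.99. Only large increases in rare defects are visible at this sample size, at any level of breakdown.

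**The case against.** The strongest reply is that this is a table-level choice in a descriptive study. The SOC sentence is an addition to the main estimate and excludes nothing, and section 7.7 leaves detail to a SAP. The ENCePP checklist in Annex 2 records that no hypothesis is tested. That stands against any claim of error in the primary analysis. It does not remove the point, because 7.7.1 chose a level and wrote it down, and where preferred terms were wanted it said so.

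Four stronger readings are tempting, and the documents do not support them.

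- *That the study cannot show a defect-specific signal.* Adverse events are coded in MedDRA, each potential anomaly is individually adjudicated, and a steering committee reviews aggregate data. The detail exists, and secondary SOC paths are not excluded.
- *That SOC is the only breakdown planned.* Section 7.7.2 is redacted, so this can be said only of the readable text.
- *That MedDRA tabulation conflicts with EUROCAT adjudication.* Section 7.1.2 uses EUROCAT to decide major, minor and/or chromosomal; MedDRA codes events. Section 7.4 says malformation data are entered from the reported verbatim and adjudication as applicable. The two serve different functions.
- *That the primary outcome was neglected.* Table 3-1 shows that the preferred-term listing for minor malformations came in by amendment because their definition and reporting vary. The difference in level has a history.

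It is also fair to object that organ-level power flatters a breakdown: the backgrounds are assumed and many groups are screened. That objection stands, and the adjusted column above shows its effect.

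**Conclusion.** The point holds in a limited form. In the readable protocol, major malformations are committed only to a SOC summary, while minor ones get the finer preferred term. On the assumption that primary SOCs are used, the SOC table would largely repeat the overall count and serve poorly to show a cluster of one defect type. The overall proportion of major malformations, which is the primary objective, is not affected, and neither is the 0.8926 power.

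The size can only be illustrated. A one-point excess has power 0.21 in the pooled test. In its own group at an assumed 0.2% background it has 0.85, falling to 0.56 with 10 groups. Across assumed backgrounds of 0.1% to 1%, the adjusted range is 0.80 to 0.21. These figures show what a table might reveal; they do not justify formal organ-level tests. The change is worth making because about 15 major cases are expected at background and listing their coded terms takes little effort.

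**What to change.** Replace the SOC sentence in 7.7.1 with wording such as:

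> Major congenital malformations will be listed by MedDRA preferred term and summarized by organ-system group, for each of the two denominators. The groups will be the EUROCAT subgroups where adjudication records them, and otherwise MedDRA HLGT/HLT. These tables are descriptive.

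If a SOC table is kept, state whether primary or secondary paths are used.

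The preferred-term listing matches what is already promised for minor malformations and needs no new data. The EUROCAT grouping may need one added field on the adjudication form, since section 7.1.2 names no subgroup output. The downside is more rows with small counts and no formal inference at organ level. Any power figure quoted in support should be labelled as resting on assumed backgrounds and shown with multiplicity.

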### 7.7.3 Case description

The cohort attrition will be presented providing the overall vs. prospective vs. retrospective number of pregnancy cases and fetuses retrieved at the time of the analysis cut-off date via maternal and paternal exposure.

In addition, the following information will be summarized

- Case disposition status (outcome known, pending, and lost to follow-up),
- Maternal characteristics (age (continuous), country/region),
- Reporter type (Health Care Professional (HCP), non-HCP).

## 7.8 Quality control

### 7.8.1 Data quality management

The standard operational procedures for pharmacovigilance will be followed to perform quality control of the data entered to the Novartis global safety database. Additional training for case processors specific to PRIM data collection and entry and additional checks will be implemented on the core data elements to ensure data quality and support for programmatic data summarization.

### 7.8.2 Data recording and document retention

Data recording and documentation retention will follow standard operating procedures defined for collection and retention of data in the Novartis global safety database.

Reporting activities will follow the SOPs related to programming in the global Novartis programming system.

## 7.9 Limitations of the research methods

The limitations of PRIM are detailed by [Geissbühler et al \(2020\)](#) and are consistent with those of voluntary post marketing report systems: under reporting, and a potential for more missing or incomplete information than in a clinical study. Spontaneous report data are collected passively relying on healthcare professionals and patients to recognize suspected adverse outcomes, collect and collate relevant information, and submit reports in the required format. Hence, the information received is often insufficient or incomplete. To reduce the potential for selection bias due to loss to follow-up (a recognized limitation of voluntary reporting systems), contact attempts via multiple contact modalities are systematically and repeatedly performed under the PRIM processes. In addition, prospective cases (where pregnancy outcome is unknown at the time of reporting) and retrospective cases will be evaluated separately given the risk of selective reporting of adverse outcomes in retrospective reporting.

A direct comparison between prevalence estimates of congenital malformation and other outcomes obtained through PRIM with external reference in the general populations is hampered by potential differences in data collection methods. Interpretation of the results of these comparisons is therefore limited. Nevertheless, the results can be put in context with a range of estimates from the general population coming from different data sources with a focus on those which use similar data collection methods as PRIM ([Geissbühler et al 2020](#)).

To evaluate the impact of exposure on the pregnancy outcomes further, exposure is stratified as exposure during peri-LMP only vs exposure only after 1st trimester. These categories may, however, be subject to selection bias. The group “exposure during peri-LMP only” excludes pregnancies with normal outcomes without any assessment of drug exposure duration (i.e., throughout the entirety of the pregnancy). On the other hand, the group “exposure only after 1st

trimester” could be subject to immortality bias. By construction, the category would not capture any event prior to 1st trimester of exposure.

While planned to be addressed in this study, not all secondary analyses ██████████ analyses may be possible to perform due to potential for underreporting, large proportion of missing or incomplete information. Finally, yet importantly, the main limitation is the inability to establish causality and the possible adjustment for known and unknown confounding factors.

## 7.10 Other aspects

A steering committee consisting of external experts such as epidemiologists, neurologists, perinatologists, pediatricians, teratologists and/or neonatologists will be formed. This steering committee will have oversight of all the Kesimpta pregnancy studies including the Kesimpta-PRIM study and will review aggregate data, data interpretation and discussion from the individual and overall Kesimpta pregnancy studies.

## 8 Protection of human subjects

This study was designed and shall be implemented and reported in accordance with the Guidelines for Good Pharmacoepidemiology Practices (GPP) of the International Society for Pharmacoepidemiology ([ISPE 2016](#)), the STROBE (Strengthening the Reporting of Observational Studies in Epidemiology) guidelines ([Vandenbroucke, et al 2007](#)), and with the ethical principles laid down in the Declaration of Helsinki.

This study is fulfilling the criteria of a ‘European Network of Centres for Pharmacoepidemiology and Pharmacovigilance (ENCePP) study’ and follows the ‘[ENCePP Code of Conduct](#)’ (European Medicines Agency 2016).

Further, this study is a secondary use of pharmacovigilance data that is collected as per good pharmacovigilance practices (GVP) guidelines and local data privacy laws and de-identified to remove all personal data.

## 9 Management and reporting of adverse events/adverse reactions

Since this study utilizes spontaneously reported data that is entered into the Novartis safety database, no additional safety data collection procedures are required.

## 10 Plans of disseminating and communicating study results

The study protocol and the results will be publicly disclosed according to the applicable regulation and the applicable Novartis SOPs.

Upon study completion and finalization of the study report, the results of this NIS may be either submitted for publication and/or posted in a publicly accessible database of results. Publications will comply with internal Novartis standards and the International Committee of Medical Journal Editors (ICMJE) guidelines.

The interim and final reports will be submitted to EMA as per the RMP commitment as a standalone procedure.

## 12 Annexes

### 12.1 Annex 1 – List of stand-alone documents

**Table 12-1 List of stand-alone documents**

| Number | Document reference number | Date      | Title   |
|---------------|----------------------------------|------------------|--|
| 1             | Type here                        | 01 February 2021 | Ofatumumab Pregnancy Baseline Follow-Up Checklist, version 1.0   |
| 2             | Type here                        | 01 February 2021 | Ofatumumab Pregnancy Outcome (Estimated Date of Delivery + one month) Follow-up Checklist, version 1.0 |
| 3             | Type here                        | 01 February 2021 | Ofatumumab Infant Health Status Follow-up Checklist, version 1.0                                       |

## 12.2 Annex 2 – ENCePP checklist for study protocols

Doc.Ref. EMA/540136/2009

### ENCEPP Checklist for Study Protocols (Revision 4)

Adopted by the ENCePP Steering Group on 15/10/2018

The European Network of Centres for Pharmacoepidemiology and Pharmacovigilance (ENCEPP) welcomes innovative designs and new methods of research. This Checklist has been developed by ENCePP to stimulate consideration of important principles when designing and writing a pharmacoepidemiological or pharmacovigilance study protocol. The Checklist is intended to promote the quality of such studies, not their uniformity. The user is also referred to the ENCePP Guide on Methodological Standards in Pharmacoepidemiology, which reviews and gives direct electronic access to guidance for research in pharmacoepidemiology and pharmacovigilance.

For each question of the Checklist, the investigator should indicate whether or not it has been addressed in the study protocol. If the answer is "Yes", the section number of the protocol where this issue has been discussed should be specified. It is possible that some questions do not apply to a particular study (for example, in the case of an innovative study design). In this case, the answer 'N/A' (Not Applicable) can be checked and the "Comments" field included for each section should be used to explain why. The "Comments" field can also be used to elaborate on a "No" answer.

This Checklist should be included as an Annex by marketing authorisation holders when submitting the protocol of a non-interventional post-authorisation safety study (PASS) to a regulatory authority (see the Guidance on the format and content of the protocol of non-interventional post-authorisation safety studies). The Checklist is a supporting document and does not replace the format of the protocol for PASS presented in the Guidance and Module VIII of the Good pharmacovigilance practices (GVP).

#### Study title:

Evaluation of pregnancy and infant outcomes in Kesimpta patients using PRenancy outcomes Intensive Monitoring (PRIM) data – The Kesimpta-PRIM study

**EU PAS Register® number:** not yet registered

**Study reference number (if applicable):** N/A

| Section 1: Milestones                | Yes                          | No                | N/A                          | Section Number |
|---|-------------------------------------|--------------------------|-------------------------------------|-----------------------|
| 1.1 Does the protocol specify timelines for |                                     |                          |                                     |                       |
| 1.1.1 Start of data collection  |  |  |             | 4                     |
| 1.1.2 End of data collection    |  |  |             | 4                     |
| 1.1.3 Progress report(s)                    |             |  |  |                       |
| 1.1.4 Interim report(s)                     |  |  |             | 4                     |
| 1.1.5 Registration in the EU PAS Register®  |  |  |             | 4                     |

 Date from which information on the first study is first recorded in the study dataset or, in the case of secondary use of data, the date from which data extraction starts.

 Date from which the analytical dataset is completely available.

| Section 1: Milestones  | Yes                          | No                | N/A               | Section Number |
|--------------------------------------|-------------------------------------|--------------------------|--------------------------|-----------------------|
| 1.1.6 Final report of study results. |  |  |  | 4                     |

Comments:

|  |
|--|
|  |
|--|

| Section 2: Research question  | Yes                          | No                | N/A                          | Section Number |
|---|-------------------------------------|--------------------------|-------------------------------------|-----------------------|
| 2.1 Does the formulation of the research question and objectives clearly explain:   |  |  |             | 6                     |
| 2.1.1 Why the study is conducted? (e.g. to address an important public health concern, a risk identified in the risk management plan, an emerging safety issue) |  |  |             | 5                     |
| 2.1.2 The objective(s) of the study?  |  |  |             | 6                     |
| 2.1.3 The target population? (i.e. population or subgroup to whom the study results are intended to be generalised)   |  |  |             | 6                     |
| 2.1.4 Which hypothesis(-es) is (are) to be tested?  |             |  |  |                       |
| 2.1.5 If applicable, that there is no a priori hypothesis?   |  |  |             | 7.7                   |

Comments:

|  |
|--|
| No hypotheses to be tested in the study, primary objective is a descriptive analysis |
|--|

| Section 3: Study design   | Yes                          | No                | N/A               | Section Number |
|---|-------------------------------------|--------------------------|--------------------------|-----------------------|
| 3.1 Is the study design described? (e.g. cohort, case-control, cross-sectional, other design)   |  |  |  | 7.1                   |
| 3.2 Does the protocol specify whether the study is based on primary, secondary or combined data collection?   |  |  |  | 7.1,7.2               |
| 3.3 Does the protocol specify measures of occurrence? (e.g., rate, risk, prevalence)  |  |  |  | 7.7                   |
| 3.4 Does the protocol specify measure(s) of association? (e.g. risk, odds ratio, excess risk, rate ratio, hazard ratio, risk/rate difference, number needed to harm (NNH))                            |  |  |  | 7.7                   |
| 3.5 Does the protocol describe the approach for the collection and reporting of adverse events/adverse reactions? (e.g. adverse events that will not be collected in case of primary data collection) |  |  |  | 9                     |

Comments:

|  |
|--|
| There will not be any measures of association due to the descriptive nature of this study. |
|--|

| Section 4: Source and study populations  | Yes                          | No                | N/A               | Section Number |
|--|-------------------------------------|--------------------------|--------------------------|-----------------------|
| 4.1 Is the source population described?  |  |  |  | 7.4                   |
| 4.2 Is the planned study population defined in terms of:   |                                     |                          |                          |                       |
| 4.2.1 Study time period  |  |  |  | 4, 7.5                |
| 4.2.2 Age and sex  |  |  |  | 7.2                   |
| 4.2.3 Country of origin  |  |  |  | 7.2                   |
| 4.2.4 Disease/indication   |  |  |  | 7.2,7.3               |
| 4.2.5 Duration of follow-up  |  |  |  | 7.4                   |
| 4.3 Does the protocol define how the study population will be sampled from the source population? (e.g. event or inclusion/exclusion criteria) |  |  |  | 7.2                   |

Comments:

|  |
|--|
|  |
|--|

| Section 5: Exposure definition and measurement  | Yes                          | No                | N/A                          | Section Number |
|---|-------------------------------------|--------------------------|-------------------------------------|-----------------------|
| 5.1 Does the protocol describe how the study exposure is defined and measured? (e.g. operational details for defining and categorising exposure, measurement of dose and duration of drug exposure) |  |  |             | 7.3.1                 |
| 5.2 Does the protocol address the validity of the exposure measurement? (e.g. precision, accuracy, use of validation sub-study)   |             |  |  |                       |
| 5.3 Is exposure categorised according to time windows?  |  |  |             | 7.3.1                 |
| 5.4 Is intensity of exposure addressed? (e.g. dose, duration)   |  |  |             | 7.3.1                 |
| 5.5 Is exposure categorised based on biological mechanism of action and taking into account the pharmacokinetics and pharmacodynamics of the drug?  |  |  |             | 7.3.1                 |
| 5.6 Is (are) (an) appropriate comparator(s) identified?   |  |  |             | 7.7                   |

Comments:

|   |
|---|
| No additional measures to ensure validity of measurement are planned. |
|---|

| Section 6: Outcome definition and measurement  | Yes                          | No                | N/A                          | Section Number |
|--|-------------------------------------|--------------------------|-------------------------------------|-----------------------|
| 6.1 Does the protocol specify the primary and secondary (if applicable) outcome(s) to be investigated?   |  |  |             | 6.1.1,
6.2.1       |
| 6.2 Does the protocol describe how the outcomes are defined and measured?  |  |  |             | 7.3.2                 |
| 6.3 Does the protocol address the validity of outcome measurement? (e.g. precision, accuracy, sensitivity, specificity, positive predictive value, use of validation sub-study)  |  |  |             | 7.4.2                 |
| 6.4 Does the protocol describe specific outcomes relevant for Health Technology Assessment? (e.g. HRQoL, QALYs, DALYS, health care services utilisation, burden of disease or treatment, compliance, disease management) |             |  |  |                       |

Comments:

No HTA-relevant outcomes

| Section 7: Bias  | Yes                          | No                | N/A               | Section Number |
|--|-------------------------------------|--------------------------|--------------------------|-----------------------|
| 7.1 Does the protocol address ways to measure confounding? (e.g. confounding by indication)                          |  |  |  | 7.7                   |
| 7.2 Does the protocol address selection bias? (e.g. healthy user/adherer bias)                                       |  |  |  | 7.9                   |
| 7.3 Does the protocol address information bias? (e.g. misclassification of exposure and outcomes, time-related bias) |  |  |  | 7.9                   |

Comments:

To be elaborated further in the SAP

| Section 8: Effect measure modification  | Yes                          | No                | N/A               | Section Number |
|---|-------------------------------------|--------------------------|--------------------------|-----------------------|
| 8.1 Does the protocol address effect modifiers? (e.g. collection of data on known effect modifiers, subgroup analyses, anticipated direction of effect) |  |  |  | 7.7                   |

Comments:

Further subgroup analyses to be specified in the SAP

| Section 9: Data sources   | Yes | No | N/A | Section Number |
|---|------------|-----------|------------|-----------------------|
| 9.1 Does the protocol describe the data source(s) used in the study for the ascertainment of: |            |           |            |                       |

| Section 9: Data sources  | Yes                          | No                | N/A                          | Section Number |
|--|-------------------------------------|--------------------------|-------------------------------------|-----------------------|
| 9.1.1 Exposure? (e.g. pharmacy dispensing, general practice prescribing, claims data, self-report, face-to-face interview)   |  |  |             | 7.4                   |
| 9.1.2 Outcomes? (e.g. clinical records, laboratory markers or values, claims data, self-report, patient interview including scales and questionnaires, vital statistics) |  |  |             | 7.4                   |
| 9.1.3 Covariates and other characteristics?  |  |  |             | 7.4                   |
| 9.2 Does the protocol describe the information available from the data source(s) on:   |                                     |                          |                                     |                       |
| 9.2.1 Exposure? (e.g. date of dispensing, drug quantity, dose, number of days of supply prescription, daily dosage, prescriber)  |  |  |             | 7.3.1                 |
| 9.2.2 Outcomes? (e.g. date of occurrence, multiple event, severity measures related to event)  |  |  |             | 7.3.2                 |
| 9.2.3 Covariates and other characteristics? (e.g. age, sex, clinical and drug use history, co-morbidity, co-medications, lifestyle)                                      |  |  |             | 7.3.3                 |
| 9.3 Is a coding system described for:  |                                     |                          |                                     |                       |
| 9.3.1 Exposure? (e.g. WHO Drug Dictionary, Anatomical Therapeutic Chemical (ATC) Classification System)  |  |  |             | 7.4                   |
| 9.3.2 Outcomes? (e.g. International Classification of Diseases (ICD), Medical Dictionary for Regulatory Activities (MedDRA))   |  |  |             | 7.4, 7.4.2            |
| 9.3.3 Covariates and other characteristics?  |  |  |             | 7.4                   |
| 9.4 Is a linkage method between data sources described? (e.g. based on a unique identifier or other)   |             |  |  |                       |

